2.1 Objectives and related endpoints

Table 2-1 Objectives and related endpoints

Objective(s)	Endpoint(s)
Primary Objective(s)	Endpoint(s) for primary objective(s)

 To demonstrate that LCZ696 is superior to individualized medical therapy for comorbidities in reducing NT-proBNP from baseline after 12 weeks of treatment To demonstrate that LCZ696 is superior to individualized medical therapy for comorbidities in improving exercise capacity as assessed by the six-minute walk test (6MWT) at Week 24 in a subset of patients 	
 Change from baseline in NT-proBNP (in log scale) at Week 12 Change from baseline in six-minute walk distance (6MWD) at Week 24
Secondary Objective(s)	Endpoint(s) for secondary objective(s)

 To compare LCZ696 to individualized medical therapy for comorbidities on mean change of KCCQ clinical summary score (CSS) at Week 24 To compare LCZ696 to individualized medical therapy for comorbidities on proportion of patients with ≥ 5-points change in KCCQ CSS at Week 24 (separate analyses for ≥ 5-points improvement and ≥ 5-points deterioration) To compare LCZ696 to individualized medical therapy for comorbidities in improving NYHA functional class at Week 24 To compare LCZ696 to individualized medical therapy for comorbidities in improving symptoms as assessed by The Short Form (36) Health Survey (SF-36) physical component summary (PCS) score at Week 24 	
 Mean change from baseline in KCCQ CSS at Week 24 Proportion of patients with ≥ 5-points deterioration in KCCQ CSS at Week 24 Proportion of patients with ≥ 5-points improvement in KCCQ CSS at Week 24 Change from baseline in NYHA functional class at Week 24 Change from baseline in SF-36 PCS score at Week 24
Exploratory Objective(s)	Endpoint(s) for exploratory objective(s)

 To compare LCZ696 to individualized medical therapy for comorbidities in reducing NT-proBNP at Week 24 	
 Change from baseline in NT-proBNP (in log scale) at Week 24

Objective(s)	Endpoint(s)

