6.4.2 Secondary efficacy assessment

The secondary efficacy variables include:

- KCCQ CSS at Week 24
- NYHA functional classification at Week 24
- SF-36 PCS score at Week 24

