- With both H_1 and H_2 rejected at the initial step, if H_3 is rejected at one-sided 0.025, the alpha will be propagated to H_4 , such that, H_4 will be tested at full alpha (one-sided 0.025). Otherwise, the testing procedure will stop.

Figure 9-1 provides graphical illustration of the sequentially rejective testing procedure.

Figure 9-1 Graphical illustration of the sequentially rejective testing procedure

Based on the above testing procedure, if applicable, H₁, H₂ and H₃ will be tested based on the corresponding MMRM models (Section 9.4.2, Section 9.5.1.1), H₄ will be tested based on the longitudinal proportional cumulative odds model (Section 9.5.1.3)

If statistical significance had been established in the mean difference in change from baseline to Week 24 for KCCQ CSS, the following responders will be analyzed accordingly, based on the longitudinal binary logistic regression models (Section 9.5.1.1), to further illustrate the clinical relevance of the observed differences in terms of proportion of responders.

- KCCQ CSS improvement (defined by at least 5 points improvement);
- KCCQ CSS deterioration (defined by at least 5 points deterioration);

No multiplicity adjustment will be done for these supportive responder analyses (i.e., the tests for the responder analyses will be performed at nominal level of one-sided 0.025).

NT-proBNP analyses

The changes from baseline in log(NT-proBNP) will be analyzed using a mixed model for repeated measures (MMRM), in which, the response variable will be the changes from baseline in log(NT-proBNP); stratum (defined by prior ACEi/ARB medication usage [ACEi, ARB, None]), region, treatment (LCZ696, individualized medical therapy), visit and treatment-by-visit interaction will be included as fixed-effect factors; baseline log(NT-proBNP), stratum-by-baseline and visit-by-baseline interactions will be included as covariates; the within-patient covariance will be modeled using an unstructured covariance matrix (a common matrix for the two treatment groups). The analysis will include all post-baseline scheduled visits up to Week 12 (Week 4, Week 12) and will be performed based on the likelihood method with an assumption of missing at random (MAR) for missing data (Siddiqui et al 2009, National Research Council 2010).

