9.8 Sample size calculation

The sample size (2500 randomized patients) has been chosen in order to provide adequate power to evaluate both primary and secondary endpoints.

With an alpha of one-sided 0.0225, the power for the NT-proBNP will range from 92% to more than 99%, to detect a relative reduction ranging from 11% to 24% in change from baseline to Week 12 in NT-proBNP, assuming a standard deviation of 0.81 for change from baseline in the

log-transformed NT-proBNP (based on PARAMOUNT-HF data of patients with baseline KCCQ CSS < 75) and an overall drop-out rate of 10%.

With an alpha of one-sided 0.0025, the power for the 6MWD will range from 90% to 99%, to detect a mean difference ranging from 22 meters to 30 meters in change from baseline to Week 24 in 6MWD, assuming a standard deviation of 120 meters (Ingle et al 2005), an overall drop-out rate of 10%, and an overall proportion of 88% for patients with B6MWD ranging from 100 meters to 450 meters.

With an alpha of one-sided 0.0225, the power for the KCCQ CSS will range from 87% to 99%, to detect a mean difference ranging from 2 points to 3 points in change from baseline to Week 24 in KCCQ CSS, assuming a standard deviation of 15.52 points for change from baseline in the KCCQ CSS (based on PARAMOUNT-HF data of patients with baseline KCCQ CSS < 75) and an overall drop-out rate of 5%.

All alpha levels in the following sample size calculations will be one-sided 0.025.

This sample size of 2500 randomized patients aims to provide a power of approximately 90%, with the one-sided alpha level of 0.025, to demonstrate a 5% responder advantage in at least 5-point deterioration for patients who are treated with LCZ696 over individualized medical therapy when assuming the proportion of patients with at least 5-point deterioration from baseline to Week 24 in the individualized medical therapy group is 20% (based on PARAMOUNT-HF data of patients with baseline KCCQ CSS < 75) and an overall 5% dropouts.

With the same assumption of the dropout rate, this sample size will also provide a power of 69% to detect a 5% responder advantage in at least 5-points improvement in the KCCQ clinical summary score for patients who are treated with LCZ696 over individualized medical therapy when assuming the proportion of patients with at least 5-points improvement from baseline to Week 24 in the individualized medical therapy group is 55% (based on PARAMOUNT-HF data of patients with baseline KCCQ CSS < 75).

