The sensitivity of power for at least 5-points deterioration in the KCCQ clinical summary score to changes in assumptions is outlined in Table 9-1.

Table 9-1 Sensitivity of power for at least 5-points deterioration in KCCQ clinical summary score to changes in assumptions for N = 2500

Assumed probability of at least 5-points deterioration			Power for at least 5-points deterioration (one-sided alpha = 0.025)			
Individualized medical therapy	LCZ696	Difference	With 5% drop-out rate	With 10% drop-out rate	With 15% drop-out rate	With 20% drop-out rate
20%	15%	-5%	90%	88%	86%	84%
35%	30%	-5%	74%	72%	69%	67%

The sensitivity of power for at least 5-points improvement in the KCCQ CSS to changes is outlined in Table 9-2.

Table 9-2 Sensitivity of power for at least 5-points improvement in KCCQ clinical summary score to changes in assumptions for N = 2500

Assumed probability of at least 5-points improvement			Power for at least 5-points improvement (one-sided alpha = 0.025)			
Individualized medical therapy	LCZ696	Difference	With 5% drop-out rate	With 10% drop-out rate	With 15% drop-out rate	With 20% drop-out rate
55%	60%	5%	69%	67%	65%	62%
41%	46%	5%	69%	67%	64%	62%

The assumed dropout rates (Table 9-1 and Table 9-2) are for the purpose of power sensitivity analysis. During the conduct of the study, all efforts will be made to reduce missing data.

For other secondary endpoints, this sample size will provide adequate powers for reasonable effect size assumptions: power of 90% for NYHA class change, assuming 14% of the patients in the comparator and 19% of the patients in the LCZ696 group are improved in NYHA class change, 6% of the patients in the comparator and 5% of the patients in the LCZ696 group are worsened in NYHA class change (based on Week 24 PARAMOUNT-HF data of patients with baseline KCCQ CSS < 75); and power of approximately 90% to detect a between treatment group mean difference of 1.4 points or more in change from baseline in SF-36 physical component summary score, assuming a standard deviation of 10-points (Edelmann et al 2013).

East 6.3 was used for the sample size calculations.

10 Ethical considerations

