#### **2.6.3.1 SF-36 physical component summary (PCS) score**

For patients who have died, the SF-36 PCS score after the death will be imputed as zero. For patients who permanently discontinue from study treatment, values collected after permanent discontinuation will generally be included in the analysis.

The changes from baseline in SF-36 PCS score will be analyzed using a MMRM model, in which, the response variable will be the changes from baseline in SF-36 PCS score; stratum (ACEi, ARB, No RASi), region, treatment (LCZ696, IMT), visit and treatment-by-visit interaction will be included as fixed-effect factors; baseline SF-36 PCS score (BPSS), BSBP, stratum-by-BPSS, stratum-by-BSBP and visit-by-BPSS interactions will be included as covariates; the within-patient covariance will be modeled using an unstructured covariance matrix (a common matrix for the two treatment groups). The analysis will include all post-baseline scheduled visits up to Week 24 (Week 16 and Week 24) and will be performed based on the likelihood method with an assumption of MAR for missing data (other than due to death).

Based on the MMRM model, the estimates and the two-sided 95% confidence intervals will be provided for the adjusted mean SF-36 PCS scores and the adjusted mean changes from baseline in the SF-36 PCS score at each post-baseline scheduled visit (Week 16 and Week 24) in both treatment groups (LCZ696 and IMT), and for the adjusted mean difference (LCZ696 minus

IMT) at each post-baseline scheduled visit (Week 16 and Week 24). The one-sided p-values will also be provided based on the MMRM model.

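### SF-36 PCS is a powered secondary endpoint outside the H1–H4 testing procedure and without a nominal label; a terminal H5 after H4 would allow a controlled result without changing the levels or powers of H1–H4

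*Protocol*

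**What the plan says.** - **Endpoint status.** Protocol Table 2-1 lists "Change from baseline in SF-36 PCS score at Week 24" among the secondary endpoints. Protocol 6.4.2 repeats it as a secondary efficacy variable, and SAP Table 1-2 agrees.
- **Power.** Protocol 9.8 opens with "The sample size (2500 randomized patients) has been chosen in order to provide adequate power to evaluate both primary and secondary endpoints". Before it turns to the KCCQ responders, NYHA and SF-36, it sets the level: "All alpha levels in the following sample size calculations will be one-sided 0.025". For SF-36 PCS it then states "power of approximately 90% to detect a between treatment group mean difference of 1.4 points or more", "assuming a standard deviation of 10-points". SAP section 3 says the same. Neither document gives a dropout rate for SF-36.
- **Testing strategy.** Protocol 9.4.2 and SAP 2.5.2 name four hypotheses: H1 (NT-proBNP), H2 (6MWD), H3 (KCCQ CSS) and H4 (NYHA). The path with both primaries rejected ends with H4, which "will be tested at full alpha (one-sided 0.025). Otherwise, the testing procedure will stop". On the other two paths H4 is also the last hypothesis. The figures are not available, but the text writes out every path.
- **SF-36 analysis.** Protocol 9.5.1.4 gives estimates and 95% confidence intervals, with no hypothesis. SAP 2.6.3.1 adds: "The one-sided p-values will also be provided based on the MMRM model".
- **Contrast.** The KCCQ responder analyses are expressly unadjusted and tested at a nominal one-sided 0.025 (Protocol 9.4.2, SAP 2.6.1.1). SF-36 PCS has no such statement.

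**The concern.** Of the secondary endpoints in Table 2-1, SF-36 PCS alone has neither a place in the testing procedure nor a stated status. KCCQ CSS is H3, NYHA is H4, and the two responder endpoints are declared nominal. Protocol 9.8 gives the NYHA and SF-36 powers in one sentence, although only NYHA can be tested under error control.

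Two things are at stake:

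- **Interpretation.** A reader of the study report who sees a one-sided SF-36 p-value below 0.025 has no rule for reading it. If it were used for a claim beside the 0.025 family, the overall one-sided error would be 1 − 0.975² = 4.9% under independence, and at most 0.025 + 0.025 = 5.0%.
- **Unused opportunity.** Whenever H4 is rejected, its alpha goes nowhere. One more hypothesis could be tested with it at no cost to the other four.

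**Working it through.** **1. Reproduce the stated power.** Inputs from Protocol 9.8: difference 1.4, SD 10, 2500 patients at 1:1, one-sided 0.025. With n per arm = 1250 × (1 − dropout),

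power = Φ(1.4 / (10·√(2/n)) − 1.960).

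| Assumed dropout | n per arm | Power at 0.025 | Power at 0.0025 |
|---|---|---|---|
| 0% | 1250 | 93.8% | 75.6% |
| 5% | 1187.5 | 92.7% | 72.7% |
| 10% | 1125 | 91.3% | 69.6% |
| 15% | 1062.5 | 89.7% | 66.3% |
| 20% | 1000 | 87.9% | 62.7% |

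The stated value of about 90% reproduces at 10% to 15% dropout.

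**2. Alpha for SF-36 PCS as written.** It is 0 on all three paths (both primaries rejected at the first step, H1 only, H2 only). The chance of a controlled SF-36 PCS result is therefore 0.

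**3. Add a terminal H5 after H4.** H5 receives alpha only once H4 has been rejected, and it sends none back. H4 sends its alpha nowhere at present, so no level for H1 to H4 changes. The levels in use never add to more than 0.025, so family-wise control is kept.

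**4. Size of the gain.** Powers at the low-end planning effects, using the same formula:

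- H1: 11% reduction, SD 0.81, 1125 per arm: 92.0% at 0.0225.
- H2: 22 m, SD 120, 1125 × 0.88 = 990 per arm: 89.8% at 0.0025 and 98.3% at 0.025.
- H3: 2 points, SD 15.52, 1187.5 per arm: 88.1% at 0.025, 87.2% at 0.0225 and 63.0% at 0.0025.
- H4: 90.2% at 0.025 (Wilcoxon calculation from the stated NYHA percentages at 5% dropout; the protocol says 90%). The noncentrality is 1.960 + 1.293 = 3.253, so power at 0.0025 is Φ(3.253 − 2.807) = 67.2%.

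Probability that H4 is rejected, by path, for independent endpoints:

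- Both primaries first: 0.920 × 0.898 × 0.881 × 0.902 = 0.657. H5 is tested at 0.025.
- H1 first, H2 on retest: 0.920 × (0.983 − 0.898) × 0.872 × 0.902 = 0.061. H5 is tested at 0.025.
- H2 only: (1 − 0.920) × 0.898 × 0.630 × 0.672 = 0.030. H5 is tested at 0.0025.

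At 10% SF-36 dropout: (0.657 + 0.061) × 0.913 + 0.030 × 0.696 = 0.677.

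Over the dropout range, with a simulation of one million draws per setting for correlation 0.3:

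| Assumed SF-36 dropout | Independent | Correlation 0.3 |
|---|---|---|
| 0% | 69.7% | 73.3% |
| 5% | 68.8% | 72.6% |
| 10% | 67.7% | 71.8% |
| 20% | 65.0% | 69.6% |

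**5. The H2-only path.** H4 is rejected this way in 3.0% of trials (independent) or 1.6% (correlation 0.3). At 10% dropout and independence this path adds only 0.030 × 0.696 = 2.1 percentage points to the SF-36 figure.

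**The case against.** The strongest reply is that nothing is wrong as written, and most of it stands.

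- **The family is defined openly.** Both documents list which hypotheses enter the strategy, and the Amendment 2 rationale says it was agreed with major Health Authorities. A secondary endpoint outside the controlled family is a legitimate choice.
- **No controlled SF-36 claim is promised.** The primary objectives are to demonstrate superiority, whereas the SF-36 objective is to compare. The KCCQ and NYHA sections refer to their hypotheses and the testing strategy; the SF-36 section does not.
- **Stated power does not imply controlled testing here.** Protocol 9.8 also gives power for the KCCQ responder analyses, which are expressly unadjusted. A reader might infer that the 90% figure is wrong, or that it promises a confirmatory test which the graph then withholds. The documents support neither reading.
- **Every finite procedure has a last node.** Alpha left over after H4 is not a defect in itself.
- **SF-36 is not the only candidate for that alpha.** On the H2-only path H1, a primary hypothesis, is still unrejected when H4 passes at 0.0025. That alpha could return to H1 instead.

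Two things remain. The SAP reports a p-value with no stated status, although the same plan labels the responder tests. And the available extension gives a large gain in what the trial can conclude, at no cost to H1 to H4.

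**Conclusion.** The point holds as an improvement of minor severity. It is not a fault in the power calculation or in error control. A reader might conclude that the trial fails to deliver on one of its objectives, but the documents commit only to a comparison on SF-36 PCS, and the plan as written provides one.

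The gain is from 0 to roughly a two-in-three or better chance of a controlled SF-36 PCS result. It rests on the low-end planning effects all being true, on an SF-36 dropout that the documents do not state (0–20% assumed), and on an assumed correlation of 0 or 0.3 between endpoints. It is a gain only if the sponsor wants a controlled statement on SF-36 PCS. The need for a label does not depend on any of these assumptions.

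**What to change.** **Preferred, before unblinding:**

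- Add H5 (SF-36 PCS change at Week 24, existing MMRM) to Protocol 9.4.2 and SAP 2.5.2 and to both figures, with one edge of weight 1 from H4. Test H5 at the level at which H4 was rejected (0.025, or 0.0025 on the H2-only path).
- State in Protocol 9.5.1.4 and SAP 2.6.3.1 that the Week 24 p-value is nominal if H5 is not reached, and that the Week 16 p-value is always nominal.
- Decide the H2-only path explicitly. The sponsor may prefer to return the 0.0025 to H1, which would then be retested at 0.0225 + 0.0025 = 0.025. The effect on the SF-36 figure is about 2 percentage points at most.
- State the dropout rate behind the SF-36 power in Protocol 9.8 and SAP section 3.

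**Cost:** a formal amendment under Protocol 11.1, and probably notification of the Health Authorities with whom the strategy was agreed. No new data or patients are needed, and no alpha is taken from H1 to H4.

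**Minimum, if the graph is not amended:** one sentence each in Protocol 9.5.1.4, Protocol 9.8, SAP 2.6.3.1 and SAP section 3, saying that the SF-36 PCS test and its stated power are nominal, as is already done for the KCCQ responder tests.

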10.1 Regulatory and ethical compliance

This clinical study was designed and shall be implemented, executed and reported in accordance with the ICH Harmonized Tripartite Guidelines for Good Clinical Practice, with applicable local regulations (including European Directive 2001/20/EC, US CFR 21, and Japanese Ministry of Health, Labor, and Welfare), and with the ethical principles laid down in the Declaration of Helsinki.

10.2 Informed consent procedures

[*]Eligible patients may only be included in the study after providing written (witnessed, where required by law or regulation), IRB/IEC-approved informed consent, or, if applicable after such consent has been provided by a legally acceptable representative(s) of the patient. In cases where the patient’s representative gives consent, the patient must be informed about the study to the extent possible given his/her understanding. If the patient is capable of doing so, he/she must indicate assent by personally signing and dating the written informed consent document or a separate assent form. Informed consent must be obtained before conducting any study-specific procedures (e.g. all of the procedures described in the protocol). The process of obtaining informed consent must be documented in the patient source documents.

[*] For **Germany only**, the first paragraph will read as follows:

Eligible patients may only be included in the study after providing written (witnessed, where

required by law or regulation) IRB/IEC-approved informed consent. He/she should indicate assent by personally signing and dating the written informed consent document. Informed consent must be obtained before conducting any study-specific procedures (i.e. all of the procedures described in the protocol). The process of obtaining informed consent should be documented in the patient source documents.

Novartis will provide to investigators in a separate document a proposed informed consent form that complies with the ICH GCP guideline and regulatory requirements and is considered appropriate for this study. Any changes to the proposed consent form suggested by the investigator must be agreed to by Novartis before submission to the IRB/IEC, and a copy of the approved version must be provided to the Novartis monitor after IRB/IEC approval.

Women of child bearing potential must be informed that taking the study treatment may involve unknown risks to the fetus if pregnancy were to occur during the study and agree that in order to participate in the study they must adhere to the contraception requirement for the duration of the study. If there is any question that the patient will not reliably comply, they must not be entered in the study.

10.3 Responsibilities of the investigator and IRB/IEC

Before initiating a trial, the investigator/institution must obtain approval/favorable opinion from the IRB/IEC for the trial protocol, written informed consent form, consent form updates, subject recruitment procedures (e.g., advertisements) and any other written information to be provided to patients/subjects. Prior to study start, the investigator is required to sign a protocol signature page confirming his/her agreement to conduct the study in accordance with these documents and all of the instructions and procedures found in this protocol and to give access to all relevant data and records to Novartis monitors, auditors, Novartis Quality Assurance representatives, designated agents of Novartis, IRBs/IECs, and regulatory authorities as required. If an inspection of the clinical site is requested by a regulatory authority, the investigator must inform Novartis immediately that this request has been made.

10.4 Publication of study protocol and results

The key design elements of this protocol will be posted in a publicly accessible database such as clinicaltrials.gov. In addition, upon study completion and finalization of the study report the results of this trial will be either submitted for publication and/or posted in a publicly accessible database of clinical trial results.

10.5 Quality Control and Quality Assurance

Novartis maintains a robust Quality Management (QM) system that includes all activities involved in quality assurance and quality control, including the assignment of roles and responsibilities, the reporting of results, and the documentation of actions and escalation of issues identified during the review of quality metrics, incidents, audits and inspections.

Audits of investigator sites, vendors, and Novartis systems are performed by Novartis Pharma Auditing and Compliance Quality Assurance, a group independent from those involved in conducting, monitoring or performing quality control of the clinical trial. The clinical audit process uses a knowledge/risk based approach.

Audits are conducted to assess GCP compliance with global and local regulatory requirements, protocols and internal SOPs, and are performed according to written Novartis processes.

11 Protocol adherence

This protocol defines the study objectives, the study procedures and the data to be collected on study participants. Additional assessments required to ensure safety of patients should be administered as deemed necessary on a case by case basis. Under no circumstances is an investigator allowed to collect additional data or conduct any additional procedures for any research related purpose involving any investigational drugs under the protocol.

Investigators ascertain they will apply due diligence to avoid protocol deviations. If an investigator feels a protocol deviation would improve the conduct of the study this must be considered a protocol amendment, and unless such an amendment is agreed upon by Novartis and approved by the IRB/IEC and health authorities, where required, it cannot be implemented.

